6.6 Benefit

Study participation may not directly benefit participants of the study especially those who do not have an actionable phenotype. It is possible however that those individuals who have an actionable phenotype may benefit from this study.

Improved drug therapy

The genotype information could lead to improved drug therapy management for select participants. For example, *CYP2D6* genotype may help to identify participants unlikely to respond to codeine, tramadol, or hydrocodone or who are at high risk for toxicity with these opiates plus oxycodone. This could lead to prescribing of alternative opiates or other non-opioid therapies more likely to reduce pain without compromising participant safety. In addition, through improved pain management and use of lower potency opioids in individuals expected to respond well to these drugs based on genotype, the study may indirectly have positive impacts on the opioid crisis by helping to reduce the individual participant opioid burden.

Similar to the above, potential benefits exist for the SSRIs based on more appropriate dosing or selection of an alternative antidepressant. Finally, participants may benefit from optimized therapy for other drugs that may have recommendations based on the panel-based pharmacogenetic testing.

Though the study participants that are randomized to the usual care/control arm have no potential to derive benefit during their participation in the clinical trial, when they complete the 6-month follow-up, they will have their genotype recorded in the EHR, whereby it could be used to guide any future relevant therapies.

6.7 Costs to the Participants

The cost of clinical genotyping and collection of PRO outcomes will be covered by the clinical trial. The cost of their drug therapy will not be covered by the trial since they would be prescribed a medication regardless of participation in the trial. However, taking part in this study may lead to added costs to the participant, specifically the costs of their care, including the physician-prescribed drug therapy, which will generally be covered by the participant's insurance (if insured), and will not be covered by the study.

6.8 Compensation to Participants

Participants will be reimbursed for their time and effort, prorated by study completion. Sites will follow local policies and procedures for amount, timing of, and mechanism for issuing compensation to participants. Participants may be reimbursed for travel or parking expenses per institutional specific policies.

7. STUDY PROCEDURES

An overview of the study procedures to be followed is presented in this section. Recruiting sites will receive training on the protocol and MOP before site activation for enrollment.

7.1 Interventions/Treatments

The intervention, genotype-guided pain or depression therapy, is intended to reflect the practices and procedures that are likely to be implemented if PGx testing were to be integrated into standard clinical practice. The intervention has two technical components: the PGx panel testing and the clinical decisions support/clinical recommendations for providers, described below. The participant and provider facing components of the intervention include the following:

Patient Participants

- The return of the PGx testing results to the participant's medical record that is analogous to typical lab results. Participants may discuss their results with their provider.

Providers

- The return of PGx testing results to the participant's provider via standard site-specific laboratory return of results methods
- Clinical decision support will be provided to all providers, how that is provided may vary. At least one of the two options below that includes drug-drug interactions, is required.
 - a. A static report/consult note with interpretation of the genetic testing results and drug-drug interactions, and treatment recommendations
 - b. Where possible, a provider prescribing alert for actionable phenotypes, triggered when a relevant opioid or SSRI medication is ordered that indicates the participant's genetic results and/or metabolizer phenotype, the predicted phenotype (i.e. efficacy of various opioid or SSRI medications), other considerations, and treatment recommendations

PGx Panel Testing

For all trials, the PGx testing panel includes two required genes: *CYP2C19* and *CYP2D6*. The list of drugs with responses affected by these genes that will be the focus of recommendations in the trial are found in **Table 1**. Reflecting the pragmatic nature of the trial, there may be site to site variability in the testing of specific variants due to site-specific institutional approvals. The minimal required set of *CYP2C19* and *CYP2D6* variants are listed in Appendix B.

Table 1. Genes to be tested and drugs with CPIC recommendations

Genes	Drugs
CYP2C19	citalopram, escitalopram, sertraline
CYP2D6	codeine, oxycodone, tramadol, hydrocodone, fluvoxamine, paroxetine

CYP2D6 phenotypes will be inferred based on the activity scoring system as shown in **Table 2 and Table 3**. The activity score value of each allele (**Table 2**) is added together to determine the total activity score for the diplotype. The activity scores are converted to phenotypes per **Table 3**. The IM phenotype will be defined as an activity score of >0 to 0.75, not >0.75 to 1.0. As there is debate about

how to define the IM phenotype, we will have an *a priori* analysis plan to determine whether participants in the usual care arm with an activity score of >0.75 to 1 (who we will define as NM) have worse pain control or depressive symptoms than NMs with an activity score > 1 to 2. If an allele is duplicated, and it is unknown which allele is duplicated, then the AS may be a ranged number, resulting in a ranged phenotype. If the ranged phenotype is NM-UM, the individual will be treated clinically as is if they were a UM.

Table 2. CYP2D6 allele to activity score

Alleles	Activity value+
*1, *2	1
*9, *14, *17, *29, *41	0.5
*10	0.25
*3, *4, *5, *6, *7, *8	0

+ Lab reported results may use older versions of CPIC guidelines for activity value definitions

Table 3. CYP2D6 phenotype by Activity Score

Inferred CYP2D6 phenotype	CYP2D6 activity score (AS)
UM	> 2.0
NM	>0.75 to 2.0
IM*	>0 to 0.75
PM	0

*This phenotype definition differences from current CPIC guidelines and may be different from what appears in the lab reported phenotypes

CYP2C19 phenotypes will be inferred from the genotypes, as shown in **Table 4**.

Table 4. CYP2C19 phenotype by genotype

Inferred CYP2C19 phenotype	Example CYP2C19 genotypes
UM	*17/*17
RM	*1/*17
NM	*1/*1
IM	*1/*2, *1/*3, *2/*17, *3/*17
PM	*2/*2, *2/*3, *3/*3

The CYP2C19 metabolizer phenotype and the CYP2D6 metabolizer phenotypes and/or activity scores will be included in the PGx testing report generated by the laboratory, which is then returned to the provider and deposited in the EMR, where available.

Clinical Decisions Support / Clinical Recommendations

Acute and Chronic Pain

Standardized clinical consult notes with or without pharmacogenetics expert consultations will be generated based on the genotype-inferred phenotype, and in the case of drugs including *CYP2D6* guidance, will include consideration of drug interactions.

For *CYP2D6*, those taking concomitantly a strong *CYP2D6* inhibitor (as defined by FDA guidance on drug interactions[28]) will be considered to have been pheno-converted to a PM and recommendations will be consistent with that for a PM. Examples of strong inhibitors include, but are not limited to: bupropion, fluoxetine and paroxetine. Moderate inhibitors include, but are not limited to: duloxetine and mirabegron and reduce *CYP2D6* activity scores by 50%, and thus the inferred phenotype will be based on the genotype activity score x 0.5. Activity scores that align with a given phenotype, and which will ultimately will be based on genotype and drug interaction data, are shown in Tables 2 and 3. A full list of strong and moderate inhibitors can be found in Appendix C.

While we will not be including oxycodone as a drug on which we will make recommendations in IMs and PMs, based on UF data and other data in the literature that make the importance of *CYP2D6* for the pain response unclear, there are data that suggest that *CYP2D6* UMs can have significant toxicities (especially respiratory depression).[1, 29-31] Thus, oxycodone will be a drug for which we will make strong recommendations about avoiding use in UMs.

Using a standardized consult note/CDS or pharmacogenetics expert consultation, recommendations will be made to avoid tramadol, hydrocodone, or codeine in PMs, IMs, and UMs and to use an alternative opioid (e.g. morphine, hydromorphone) or non-opioid (e.g. NSAID), as noted in Table 5. Consideration of tramadol as the first line opioid will be recommended for NMs. While not part of the primary hypothesis, for safety reasons, avoidance of oxycodone will also be recommended in UMs.

Additionally, where possible, the CDS will include a provider alert for actionable phenotypes, triggered when a relevant opioid medication is ordered that indicates the participant's genetic results, the predicted phenotype, other considerations, and treatment recommendations.

Table 5. CDS summary for acute and chronic pain treatments

Treatment	CYP2D6 Phenotypes				
	Ultra-rapid	Normal to Ultra-Rapid	Normal*	Intermediate**	Poor
Tramadol	Avoid	Avoid	Preferred opioid	Avoid	Avoid
Codeine	Avoid	Avoid	Acceptable	Avoid	Avoid
Hydrocodone	Avoid	Avoid	Acceptable	Avoid	Avoid
Oxycodone	Avoid	Avoid	Acceptable	Acceptable	Acceptable

*Defined as activity score >0.75 and ≤ 2.0

**Defined as activity score >0 and ≤ 0.75

Depression

Clinical decision support in the form of computerized alerts, standardized clinical consult notes, and/or pharmacist consultations will be generated to guide prescribers on dosing or selection of SSRIs or selection of alternate antidepressants based on predicted phenotype. Recommendations on drug choice and starting dose will be made in accordance with CPIC guidelines and/or FDA label information for paroxetine, fluvoxamine, citalopram, escitalopram, and sertraline, as outlined in Table 6. Drug-drug interactions leading to pheno-conversion will be incorporated into recommendations. For CYP2D6, concomitant use of a strong inhibitor (listed above) will result in a predicted phenotype of poor metabolizer, and the effect of concomitant moderate inhibitor (listed above) will be estimated by multiplying the CYP2D6 activity score by 0.5.

Table 6. CDS summary for antidepressant medications

	CYP2D6 Phenotypes				
	Ultra-rapid	Normal to Ultra-rapid	Normal	Intermediate	Poor
Paroxetine	Avoid	Avoid	Acceptable	Acceptable	Avoid or 50% Dose Reduction*
Fluvoxamine	No recommendation	No recommendation	Acceptable	Acceptable	Avoid or 25-50% Dose Reduction*
	CYP2C19 Phenotypes				
	Ultra-rapid and Rapid		Normal	Intermediate	Poor
Citalopram	Avoid		Acceptable	Acceptable	Avoid or 50% Reduction**
Escitalopram	Avoid		Acceptable	Acceptable	Avoid or 50% Reduction*
Sertraline	Monitor for Non-response		Acceptable	Acceptable	Avoid or 50% Reduction*

* Dose reductions refer to starting dose of medication; Avoid refers to recommendation to switch to a drug not predominantly metabolized by the listed drug metabolizing enzyme. No recommendation refers to a scenario where CDS is not triggered but the drug is also not offered as an alternative given the phenotype.

** Per the FDA warning, citalopram 20 mg/day is the maximum recommended dose in CYP2C19 poor metabolizers due to the risk of QT prolongation

Context of the intervention implementations

Reflecting the pragmatic nature of the clinical trial, the intervention may be implemented in environments in which there are existing PGx testing and CDS. The PGx testing may be completed as part of larger, CLIA validated, PGx panel that include optional gene-drug pairs (Table 7). Additionally, clinical decision support may be in place for the study gene-drug pairs as well as other CPIC drug-gene pairs and/or other drugs affected by the study genes.

Table 7. PGx panel genes and drugs with CPIC recommendations

Genes	Drugs
CYP2C19 (Required)	amitriptyline, clopidogrel, clomipramine, doxepin, imipramine, trimipramine, voriconazole, omeprazole, esomeprazole, pantoprazole, lansoprazole, dexlansoprazole
CYP2D6 (Required)	amitriptyline, clomipramine, desipramine, doxepin, imipramine, nortriptyline, ondansetron, trimipramine, tropisetron
CYP2C9	warfarin, phenytoin
CYP3A5	Tacrolimus
SLCO1B1	Simvastatin
TPMT	azathioprine, mercaptopurine, thioguanine
NUDT15	azathioprine, mercaptopurine, thioguanine
VKORC1	Warfarin
CYP4F2	Warfarin

7.2 Baseline Participant Assessments

All study participants will complete baseline surveys for demographics and participant reported outcomes (PROs) (see Table 8 for details). These data will be collected by the study coordinator in person or alternatively by using telephone, email, or text.

Baseline data will be collected for the Chronic Pain and Depression trials following consent, for the Acute pain trial, survey data will be collected before surgery. The type of surgery information will be collected after the completed procedure.

Participant demographics – including but not limited to age, sex, gender, race, Hispanic/Latino ethnicity (Yes or no), and smoking status will be administered at baseline as a survey.

Past medical history – A snapshot of the participant's medical history. See MOP for details.

Baseline medications - Participant medications will be collected through the EHR and/or participant self-report. See MOP for details.

7.3 Follow-up Participant Assessments

The event that starts the post-intervention data collection timing are as follows.

Acute Pain:

- Date of surgery (intervention and control arms)

Chronic Pain and Depression:

- Intervention arm: When the pharmacogenetics results are returned to the provider and deposited in the EMR
- Control arm: At date of DNA sample collection plus one week, where one week reflects the average time from sample collection to returning the results to the EHR
- Note: There will be variability in time the results are returned to provider and when genotype-guided therapy is delivered to the participant, time from results being available to the next provider-participant interaction (e.g. email, clinic visit, new prescription order, phone visit, etc.) will be recorded by study personnel.

Post intervention assessment collection may be done by the University of Florida College of PharmacyCall Center. The center agents will be trained survey collectors*, using an IRB approved telephone script. The collected survey responses will be entered into the study database. If preferred, the participant will have the option to complete the study follow-up survey by a URL link sent by text (to mobile phone) or email and captured in REDCap database

In the event that the call center is unable to reach a participant, local study coordinators may contact participants to facilitate completion of the follow-up surveys.

Data will be collected in the following timeframes*:

- Acute pain: 10 days, 1 month, 3 months, and 6 months post-surgery
- Chronic pain and depression: 1-month, 3 months, and 6 months post return of results for the intervention arm, and post baseline assessments for the control arm.

*See *MOP for call center agents and survey collection interval windows*

All Trials

PROMIS 43 – Adults (≥ 18 years of age) will complete a 43-question survey assessing well-being and sub domains: pain interference, physical function, sleep disturbance, social role and activities functioning, fatigue, anxiety, and depression.[32] This survey will be administered to adult participants at baseline, 1-month, 3-months, and 6-months post-surgery (acute pain), or baseline, 1-month, 3-months, and 6-months post return of results (chronic pain, depression).

PROMIS pediatrics 37 – Pediatric study participants (ages 8-17) will complete a 37-question survey assessing pediatric well-being and sub domains: pain interference, physical function, sleep disturbance, social role and activities functioning, fatigue, anxiety, and depression. This survey will be administered to pediatric participants at baseline, 1-month, 3-months, and 6-months post-surgery (acute pain), or baseline, 1 month, 3 months, and 6 months post return of results (depression).

Health care utilization – Survey of the number of significant cost driver health care encounters (e.g. hospitalizations, clinic visits, etc.). This survey will be administered to participants at 10-day, 1-month, 3-months, and 6-months post-surgery (acute pain), or baseline, 1-month, 3-months, and 6-months post return of results (chronic pain, depression).

Medications - Participant medications will be collected using patient surveys at baseline and the primary endpoint time points: 10-days for Acute Pain and 3-months for Depression and Chronic pain.

Productivity loss – Survey of loss of work the time and pay lost due to the participant's depression or pain. This survey will be administered to participants at 1-month, 3-months, and 6-months post-surgery (acute pain), or 1-month, 3-months, and 6-months post return of results (chronic pain, depression).

Acute Pain:

PROMIS Numeric Rating Scale - Pain Intensity - An 11-point numeric scale ranging from 0 (no pain) to 10 (worst possible pain) for average pain. This survey will be administered to all participants at baseline, 10 days, 1-month, 3-months, and 6-months post-surgery.

PROMIS pain intensity scale – A participant completed 3-question survey of average pain over the last 7 days, worst pain over the last 7 days, and current pain. Each question is on a 1-5 integer scale, the higher the value, the more intense the pain. This survey will be administered to all participants at baseline, 10 days, 1-month, 3-months, and 6-months post-surgery.

Opioid consumption questionnaire – A participant completed survey of pain prescription medication consumption, including the type of opioid pain medication, number of pills dispensed, if a refill has been obtained, and the number of pills left for each opioid pain medication selected. This survey will be administered to all participants at 10 days and 1-month post-surgery.

PROMIS prescription medication mis-use scale - A participant completed survey of prescription medication misuse over the past 3 months. The survey is comprised of 7 questions on a 5-point ordinal scale of never/rarely/sometimes/frequently/almost always or not at all/a little bit/somewhat/quite a bit/very much[33]. This survey will be administered at baseline, 3-months, and 6-months post-surgery.

PROMIS Item Bank v2.0 Mobility – A participant completed survey of the participant's level of difficulty in completing different physical activities such as standing unassisted, walking, and sprinting or activities that their health currently limits. The survey is comprised of 15 questions, each answered on a 5-point scale ranging from without difficulty to unable to do, or not at all through cannot do[34]. This survey will be administered at baseline, 10 days, 1-month, 3-months, and 6-months post-surgery to the adult participants.

PROMIS Pediatric Mobility – Short Form 8a – A participant completed 8 item survey of difficulty in completing different physical activities such as getting up from the floor, standing on tiptoes, and ability to do sports and exercises that their peers can complete [35]. The survey will be administered at baseline, 10 days, 1-month, 3-months, and 6-months post-surgery to the pediatric participants.

Acute pain specific health care utilization – A participant completed survey of hospital length of stay for the surgical admission, administered at 10 days post-surgery.

Opioid side effects – A participant completed survey of common opioid side effects experienced and the extent to which those side effects bothered the participant. This survey will be administered at baseline, 10 days, 1-month, 3-months, and 6-months post-surgery.

Opioid persistence - Whether or not the participant had an opioid prescription refill 90 – 180 days post-surgery. This survey will be administered to participants at 6 months post-surgery.

Chronic Pain:

PROMIS pain intensity scale – A participant completed 3-question survey of average pain over the last 7 days, worst pain over the last 7 days, and current pain. Each question is on a 1-5 integer scale, the

higher the value, the more intense the pain. This survey will be administered at baseline, 1 month, 3 months, and 6 months post return of results.

PROMIS prescription pain medication mis-use scale - A participant completed survey of prescription medication misuse over the past 30 days. The survey is comprised of 7 questions on a 5-point ordinal scale of never/rarely/sometimes/frequently/almost always or not at all/a little bit/somewhat/quite a bit/very much[33]. This survey will be administered at baseline, 3 months, and 6 months post return of results.

PROMIS emotional distress depression 8b survey - A participant completed eight question survey assessing frequency of depression symptoms over the past 7 days[36]. This survey will be administered at baseline, 1 month, 3 months, and 6 months post return of results to the adult participants.

Opioid side effects – A participant completed survey of common opioid side effects experienced and the extent to which those side effects bothered the participant. This survey will be administered at baseline, 3 months, and 6 months post return of results to the adult participants.

Depression:

PROMIS emotional distress depression 8b survey - A participant completed eight question survey assessing frequency of depression symptoms over the past 7 days[36]. This survey will be administered at baseline, 1 month, 3 months, and 6 months post return of results to the adult participants.

PROMIS Pediatric Depressive Symptoms Short Form 8a- A pediatric (ages 8-17 years) participant completed eight question survey assessing frequency of depression symptoms over the past 7 days[37]. This survey will be administered at baseline, 3 months, and 6 months post return of results to the pediatric study participants .

Patient Health Questionnaire-8 – An 8 item survey completed by the participant assessing depression symptoms over the last two weeks. This survey will be administered at baseline, 3 months, and 6 months post return of results[38].

Antidepressant side effects – A participant completed survey of relevant antidepressant side effects. This survey will be administered at baseline, 1 month, 3 months, and 6 months post return of results.

Voils Medication Adherence - A participant completed three question survey, 5-point scale survey assessing participant medication adherence[39]. This survey will be administered to depression trial participants at baseline, 1 month, 3-months and 6 months post return of results.

All of the PROMIS® surveys can be found online[40].

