3. ENDPOINTS

3.1 Primary Endpoint(s)

Acute pain: The primary endpoint for the acute pain study is the SIA score, a composite of pain and opioid usage, at 10 days post-surgical procedure. See Appendix A for the SIA score rationale.

Chronic pain: The primary endpoint for the chronic pain study is change in composite pain intensity score, assessed using the PROMIS pain intensity survey, from baseline to 3 months post return of genetic testing results to the provider.

Depression: The primary endpoint for the depression study is change in depression score, assessed using the PROMIS Emotional Distress - Depression 8b survey (adults) or PROMIS pediatric depressive symptoms (pediatric), from baseline to 3 months post return of genetic testing results to provider.

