7.4 Specimen Collection

DNA sample collection can be whole blood by venipuncture, saliva, buccal swab, or mouthwash, whichever is most appropriate for the site or study participant preference. The sample collection can occur in person or by mailed kits after consenting.

Once sample collection is completed, participants are randomized to a trial Control or Intervention arm. All DNA sample types and collection processes are detailed in the MOP.

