7.5 Specimen Transfer and Genetic Testing Procedures

All collected specimens will be clearly marked with two patient identifiers (CLIA requirement). Samples from the Intervention arm participants will be processed, using analytically validated PGx testing procedures (see Table 1 for gene and variant list). For Control arm samples, designated laboratories will either extract DNA after sample receipt, and store the DNA for later analysis or store the sample and extract DNA after the Control participant has completed the 6-month follow-up assessment. After the Control participant has completed the 6-month follow-up assessment, Control Arm samples will be processed using analytically validated procedures. Details of sample storage and transport will be presented in the MOP.

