participants, we will conduct a subset analysis comparing change in depression T-scores from baseline to 3-month follow-up in the Intervention group subset with either CYP2D6 PM or UM or CYP2C19 PM, RM or UM phenotypes to the Control group subset with CYP2D6 PM or UM or CYP2C19 PM, RM, or UM phenotypes. Participants that have other CYP2D6 or CYP2C19 phenotypes will not be included. Pediatric depression T-scores will be transformed to the adult scale using a published crosswalk for a combined analysis. The baseline to 3-month change in depression T-scores of the Intervention CYP2D6 PM/UM or CYP2C19 PM/RM/UM group will be compared to the baseline to 3-month change in depression T-scores of the Control CYP2D6 PM/UM or CYP2C19 PM/RM/UM subgroup using a two-sided two-sample t-test with a type 1 error of 0.049. This primary analysis will be conducted according to a modified intent-to-treat design, with participants analyzed and endpoints attributed according to the treatment arm to which the participants were randomized, regardless of subsequent crossover or post-randomization medical care.

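### Section 7.3 states two different control-arm start points for follow-up in the chronic pain and depression trials; if the second were followed, the arms' 3-month surveys would be about a week apart

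*Combined protocol and SAP*

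**What the plan says.** Section 7.3 opens with the events that start follow-up timing. In the chronic pain and depression trials the intervention-arm event is the return of results to the provider and the EMR. The other arm's rule is: "Control arm: At date of DNA sample collection plus one week". The plan explains that week as the mean turnaround between sampling and a result being on file.

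Later in section 7.3, the list of survey timeframes gives 1, 3 and 6 months "post return of results for the intervention arm, and post baseline assessments for the control arm". The intervention anchor is the same in both places; the control anchor is not.

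Other places that bear on timing:

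- Section 3.1 defines the chronic pain primary endpoint as change "from baseline to 3 months post return of genetic testing results to the provider", and the depression endpoint in near-identical terms. It gives no rule for controls.
- The chronic pain and depression instrument entries in 7.3 also count from return of results.
- Section 7.5: "After the Control participant has completed the 6-month follow-up assessment, Control Arm samples will be processed using analytically validated procedures". Controls therefore have no result date at 3 months.
- Section 7.2: "Baseline data will be collected for the Chronic Pain and Depression trials following consent". Section 7.4: "The sample collection can occur in person or by mailed kits after consenting". Neither fixes the interval between baseline and sample.
- Table 8 gives 3 months ± 14 days without naming an anchor.
- The legend to Figure 1 says that the figure marks Time 0, but the figure is not shown in the text available here.

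**The concern.** Both primary endpoints are change from baseline to 3 months, and section 10.4 compares the arms without adjustment. For depression the comparison is made "using a two-sided two-sample t-test with a type 1 error of 0.049"; for chronic pain it is the same test or a Mann-Whitney test.

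The one-week offset keeps elapsed time since baseline equal, on average, in the two arms. The second statement removes that offset from the control arm only. If it were followed, intervention participants would on average have longer to improve before the 3-month survey. Any improvement that both arms share over the extra days would enter the between-arm difference, and a larger sample would not remove it. The contradiction concerns the time zero of two primary endpoints.

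**Working it through.** **Inputs from the documents.** Mean lag from sample to result L = 7 days (7.3). Alpha 0.049; 134 per arm and effect size 0.40 in chronic pain; 271 per arm and 0.28 in depression (10.1, Table 9). Those sample sizes reproduce: the two-sample formula at 90% power gives 133 and 270 per arm. The timing point does not depend on them.

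**Step 1: target dates.** Put baseline at day 0, take 3 months as 91 days, and let s = sample date minus baseline date.

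- Intervention: s + L + 91.
- Control, first statement: s + 7 + 91. Gap between arms = L − 7, which is 0 at the stated mean lag. This confirms that the offset aligns the arms on average, provided that mean turnaround is one week and baseline timing does not depend on arm.
- Control, second statement: 91. Gap = s + L = s + 7.

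| s (days) | Intervention target | Control target, first statement | Control target, second statement | Gap, second statement |
|---|---|---|---|---|
| −7 | 91 | 91 | 91 | 0 |
| 0 | 98 | 98 | 91 | 7 |
| 7 | 105 | 105 | 91 | 14 |

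The documents do not give s, so the same-day case is an assumption. Mailed kits could make s positive.

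**Step 2: bias at a 7-day gap.** The documents give no rate of change. Assumption: both arms improve by A = 0.2 to 0.5 SD over 91 days.

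- Linear course: bias = A × 7/91. This gives 0.2 × 7/91 = 0.015 SD and 0.5 × 7/91 = 0.038 SD.
- Levelling off with time constant τ = 42 or 84 days: bias = A/(1 − e^(−91/τ)) × (e^(−91/τ) − e^(−98/τ)).
  - Lowest (A = 0.2, τ = 42): 0.2/0.8854 × (0.1146 − 0.0970) = 0.004 SD.
  - Highest (A = 0.5, τ = 84): 0.5/0.6615 × (0.3385 − 0.3114) = 0.020 SD.

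**Step 3: consequence.** The standard error of the difference is √(2/271) = 0.086 SD in depression and √(2/134) = 0.122 SD in chronic pain. Rejection under no treatment effect is from the noncentral t distribution, two-sided at 0.049.

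| Course over 91 days | Bias (SD) | Share of 0.28 / 0.40 | Rejection, depression | Rejection, chronic pain |
|---|---|---|---|---|
| Levelling off, lowest | 0.004 | 1.4% / 1.0% | 4.9% | 4.9% |
| Levelling off, highest | 0.020 | 7.3% / 5.1% | 5.5% | 5.2% |
| Linear, A = 0.5 | 0.038 | 13.7% / 9.6% | 7.2% | 6.0% |

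With a zero gap or no common improvement, the bias is zero and the level stays at 4.9%.

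**The case against.** The strongest reply is that section 7.3 already contains the governing rule. Its start-event list is introduced as what sets the timing, is specific to each arm, and explains the week. The later phrase sits in a list of survey timeframes footnoted to the MOP for collection windows. It may be a leftover: the amendment table records that section 7.8 was corrected from baseline to time-zero, which suggests the same slip in 7.3. Figure 1 or the MOP may settle the matter. All of this stands, and it makes an editorial inconsistency more likely than a deliberate choice. It does not remove the contradiction, because no visible text gives one clause precedence.

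Four stronger readings are tempting and are not supported:

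- *That controls were in fact followed from baseline.* Nothing in the documents shows this.
- *That the type 1 error is materially inflated.* That needs the second clause to be followed, the largest assumed gain and a strictly linear course. Gaps longer than 7 days need, in addition, a sample-to-baseline interval that the documents do not give.
- *That the ± 14-day window would hide the shift because 7 is less than 14.* Table 8 names no anchor. If windows run from each arm's own time zero, a wrong anchor goes unflagged whatever its size.
- *That section 3.1 is a separate defect.* Return of results cannot apply literally to controls, but the sample-plus-one-week rule supplies the stand-in date.

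It is also fair to say that new wording cannot re-time surveys already collected.

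**Conclusion.** The contradiction is certain on the visible text; its effect is conditional and probably small. Under the sample-plus-one-week rule the average gap is zero, provided the stated mean turnaround holds and baseline timing is the same in both arms. Under the post-baseline rule it is about 7 days if baseline and sample coincide. The resulting bias of about 0.004 to 0.02 SD, or at most about 0.04 SD on a linear course, rests on an assumed common gain of 0.2 to 0.5 SD. The documents support neither that gain nor the same-day assumption. A reader should not infer that either trial is biased, only that the protocol leaves the control-arm time zero of two primary endpoints open to two readings. It should be corrected because the correction is cheap.

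**What to change.** In the timeframe list of 7.3, replace "post return of results for the intervention arm, and post baseline assessments for the control arm" with: *post time zero as defined above for each arm*. Keep the DNA sample date plus one week as the only control-arm time zero, and carry the time-zero wording into section 3.1 and the instrument entries that count from return of results. Check that Figure 1 and the MOP agree.

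Because surveys may already have been collected, also report for each trial:

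- by arm, the actual days from baseline to the 3-month survey;
- in the intervention arm, the days from sample to result.

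The first shows whether a gap exists, and the second whether one week was the right average. The cost is a few wording changes and one descriptive table per trial. No new data are needed if the baseline, sample, result and survey dates are recorded. The intervention, the intervention-arm clock and the primary test are unchanged.
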